From Visit 2 for roll-over patients ≥ 26 weeks and from Visit 3 for new patients and for roll-over patients < 26 weeks, urine dipstick pregnancy tests will be provided with pregnancy test diary card when needed. Use of pregnancy test diary card will be explained with the patient / parent(s)/legal guardian and training will be repeated as needed. The pregnancy test diary card will be used to support the record of the date and result of test(s) between consecutive visits. Pregnancy test diary card will be reviewed at clinic visits. In case a positive test is reported the sponsor should be contacted immediately. Refer to [Section 3.3.4.1](#) for further instructions. Refer to [Section 5.2.7.2.3](#) for detailed information on event reporting in case of pregnancy.
14. [REDACTED]
15. **For new patients:** Order of lung function measurements: 1. FVC followed by patient's rest; 2. DLCO.
For roll-over patients, DLCO not applicable.
For all patients: after Visit 2 FVC measurements to be done at the same time each visit (+/- 90 min), with reference time at Visit 2.
16. [REDACTED]
17. Interactive Response Technology (IRT) should be notified upon obtaining informed consent.

18.

Please refer to [Appendix 10.1](#) for details.

19.

20.

21. Bone imaging. Please refer to [Section 5.2.5](#) and to the image acquisition guideline available in the ISF for details. For patients aged 19 and older, please see additional information at the end of the footnote.

For new patients: Bone imaging is required for all new patients who qualified for assignment of nintedanib treatment at Visit 2 as baseline. If it's not possible to conduct the baseline bone imaging at Visit 2, the procedure can be done in the 2 weeks immediately after the visit (until D15).

Imaging follow-up will be conducted only in patients with open physes at predefined time points. Imaging follow-up will be conducted, if applicable, at 12 weeks, 24 weeks, 36 weeks, 52 weeks, 76 weeks, 104 weeks, 128 weeks, 156 weeks, and every 24 weeks thereafter until the end of study or closure of the physes. If it's not possible to conduct the follow-up at the predefined time points, the procedure can be done within 1 week before and after this time point with always minimum of 10 weeks (during the first year)/22 weeks (thereafter) and always maximum of 16 weeks (during the first year)/28 weeks (thereafter) between 2 procedures.

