For all patients, if the follow-up procedure cannot be conducted at least every 16 weeks (during the first year)/28 weeks (thereafter year), the study treatment of this individual patient needs to be interrupted upon discussion with the sponsor (except at the one-time alignment with clinic visits mentioned above for roll-over patients).

For all patients, timepoints may be adapted on a case-by-case basis after discussion with the sponsor if appropriate for patient's safety.

23. Dental imaging. Please refer to [Section 5.2.6](#) and to the image acquisition guideline available in the ISF for details.

For new patients: Dental imaging is required according to protocol requirements in all patients who qualified for assignment of nintedanib treatment at baseline (Visit 2). If it's not possible to conduct the dental imaging on the day of the Visit 2, the procedure can be done in the 2 weeks immediately after the visit (until D15).

Follow-up will be conducted, if applicable, at 24 weeks, 52 weeks, 104 weeks, 156 weeks, and every 48 weeks thereafter until the end of the study. If it's not possible to conduct the follow-up at the predefined time points, the procedure can be done within 1 week before and after this time point with always a minimum of 22 weeks (during the first year)/46 weeks (thereafter) and always a maximum of 28 weeks (during the first year)/52 weeks (thereafter) between 2 procedures.

For roll-over patients: Previous dental imaging at 1199-0337 EoT or within 24 weeks prior EoT/Visit 1/Visit 2 should be used as baseline in the analyses of dental imaging (for scheduling of follow-up procedures see next paragraph). If a previous dental imaging is not available, this dental imaging should be conducted at Visit 2. If it's not possible to conduct the dental imaging on the day of the Visit 2, the procedure can be done in the 2 weeks immediately after the visit (until D15).

Irrespective of scheduled visits, follow-up will be conducted, every 24 weeks in the year after the start of the trial medication in the parent trial (when applicable) and every 48 weeks thereafter until the end of the study.

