If it's not possible to conduct the follow-up at the predefined time point, the procedure can be done within 2 weeks before or 4 weeks after this time point with always a minimum of 22 weeks (during the first year after the start of the trial medication in the parent trial)/46 weeks (thereafter) and always a maximum of 28 weeks (during the first year after the start of the trial medication in the parent trial)/52 weeks (thereafter) between 2 procedures.

Preponement or postponement of one follow-up procedure by 2 months to the planned timepoint will be allowed once to align this procedure and the subsequent ones with the regular clinic visits planned in the protocol. After this alignment, the acceptable time window will be +/-1 week for this procedure (as for new patients).

For all patients, if the follow-up procedure cannot be conducted at least every 28 weeks (during the first year)/52 weeks (thereafter), the study treatment of this individual patient needs to be interrupted upon discussion with the sponsor (except for the one-time alignment with clinic visits mentioned above for roll-over patients).

For all patients, timepoints may be adapted on a case-by-case basis after discussion with the sponsor if appropriate for patient's safety.

24. Patients who discontinue trial treatment prematurely should undergo the End of Treatment (EoT) visit as soon as possible.

At the EoT visit:

- the MRI/x-ray should not be repeated if the last MRI/x-ray was conducted within 24 weeks,
- the dental examination will not be repeated if the last examination was conducted within 12 weeks and
- the dental imaging will not be repeated if the last examination was conducted within 24 weeks.

If EoT occurs before Visit 15 (week 156), roll-over patients will be asked to remain in the study and to return to all regularly scheduled visits until week 156. New patients who prematurely discontinued trial drug will be asked to remain in the study and to return to all regularly scheduled visits until the overall end of trial.

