At future off-treatment visits, all assessments [REDACTED], and IRT call/notification will be performed. The first visit after the EoT visit will be skipped if the EoT visit occurs within 4 weeks prior to scheduled visit but if MRI/x-ray and/or dental examinations/imaging were planned at this visit, then they should be performed as planned. Only one additional regular follow-up for bone imaging and for dental imaging procedures will be needed after the EOT visit if there is no pathological finding. If there is a pathological finding, follow-up procedures will be conducted on individual basis upon discussion with the sponsor and with the investigator. Follow-up procedures for clinical dental examination will be conducted as initially planned by the protocol. Urine pregnancy tests at home (for female patients) are only required to be continued every 4 weeks for the 3 months after last trial drug intake.

25. For patients who discontinue trial treatment prematurely and are not able to complete the scheduled visits, a follow-up (FU) visit should be planned 28 days after EoT.

If the EoT visit has been delayed and has been done 28 days or more after the treatment discontinuation, the follow-up (FU) visit can be skipped.

In addition, every attempt will be made to get information on vital status, when applicable, at 24, 52, 76, 104, 128, 156, and every 24 weeks thereafter until the end of the study and for new patients at EoS. Please see [Section 5.2.7.2.1](#)

26. End of Study (EoS), synonym for individual patient's end of trial. Height, weight or safety laboratory test will be repeated at EoS visit in case of clinically relevant change at EoT. In exceptional cases, when the patient is not able to come at site for medical reason, the EoS visit can be replaced by a phone call. If the EoT visit has been delayed and has been done 28 days or more after the treatment discontinuation, the EoS visit can be skipped.
27. After the individual patient's end of the trial the investigator should report only any occurrence of cancer, study treatment related Serious Adverse Events (SAEs) and study treatment related Adverse Event of Special Interests (AESIs) of which the investigator may become aware of by any means of communication, e.g. phone call. Those AEs should be reported on the BI SAE form, but not on the eCRF. Please see [Section 5.2.7.2.1](#).

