	
(degeneration and loss of odontoblasts and ameloblasts with consecutive structural changes of enamel and cementum) of the continuously growing incisors often accompanied by dental fractures, hemorrhages and necroses in the pulp). Changes occurred only during the growth phase of the teeth.
	
weeks thereafter, taking in account, for roll-over patients, the participation in the parent trial. Please refer to Flow Chart footnotes and to CTP Section 5.2.6 for more details.
 
Expedited reporting of stunted growth identified on dental imaging (AESI).
 
Regular evaluation by paediatric dentistry expert, with panoramic x-ray at baseline and and regular follow-up conducted at predefined time points. The follow-up dental imagings will be planned, irrespective of scheduled visits, in order to respect the frequency of around every 24 weeks for first year and around every 48 weeks thereafter, taking in account, for roll-over patients, the participation in the parent trial. Please refer to Flow Chart footnotes and to CTP Section 5.2.6 for more details.
 
Regular evaluation by SMC.

Trial procedures		
Radiation exposure	Required to monitor potential risk associated with study drug and confirm patient eligibility.	
State of the art radiologic methods required, x-rays of epiphyseal growth plates only if MRI not possible in individual patients.
 
Regular dental examination and panoramic x-ray at minimum time interval required to ensure safety.
 
For new patients: HRCT at baseline required only if acceptable HRCT not available within 12 months of Visit 1.

Potential risks of clinical relevance for this trial	Summary of data, rationale for the risk	Mitigation strategy
		 
Bone MRI/x-ray required with always minimum 10 weeks (first year)/22 weeks (thereafter) and dental X-ray required with always minimum 22 weeks (first year)/46 weeks (thereafter) from the previous procedure, taking into account, for roll-over patients, the participation in the parent trial (except at the one time alignment of these safety procedures with clinic visits). Similarly, bone MRI/x-ray at EoT required only if previous MRI/x-ray not available within 12 weeks in the first year, 24 weeks thereafter. Timepoints may be adapted on a case-by-case basis after discussion with the sponsor if appropriate for patient's safety.
 
Panoramic x-ray at EoT required only if previous panoramic x-ray not available within 24 weeks.

Others risks		

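### For patients who stop early, Flow Chart footnote 24 can call for two panoramic x-rays within 4 weeks, against the protocol's own minimum interval of 46 weeks (22 in the first year)

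*Protocol*

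**What the plan says.** **Schedule.** Footnote 23 places panoramic x-rays for new patients at weeks 24, 52, 104 and 156, and 48-weekly after that. Roll-over patients go to 48-week spacing after the first year from the start of parent-trial medication.

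**Minimum interval.** Footnote 23 limits the spacing for new patients to "always a minimum of 22 weeks (during the first year)/46 weeks (thereafter") and repeats the 22/46 pair for roll-over patients. Section 5.2.6 gives the same pair. The radiation row of Table 1.4.2:1 lists it as mitigation: "dental X-ray required with always minimum 22 weeks (first year)/46 weeks (thereafter) from the previous procedure". The exception attached to that sentence is "except at the one time alignment of these safety procedures with clinic visits".

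**EoT image.** Footnote 24 and Section 6.2.2 omit the EoT panoramic x-ray only when the last is no more than 24 weeks old. Table 1.4.2:1 agrees: "Panoramic x-ray at EoT required only if previous panoramic x-ray not available within 24 weeks".

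**After EoT.** Footnote 24 skips the first post-EoT visit if EoT fell in the 4 weeks before it, "but if MRI/x-ray and/or dental examinations/imaging were planned at this visit, then they should be performed as planned". With no pathological finding, one further regular bone image and one further regular dental image are required after EoT.

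**Flexibility.** Footnotes 21 and 23, Sections 5.2.5 and 5.2.6 and Table 1.4.2:1 let time points be adapted for individual patients after discussion with the sponsor.

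**The concern.** The EoT rule measures only backwards, to the previous image. The planned-imaging sentence in footnote 24 then keeps the next image on its date, whether or not an image has just been taken at EoT. Together they can produce two panoramic x-rays of a child a few weeks apart, although the protocol presents the minimum interval as its protection against radiation exposure. A site that follows footnote 24 breaks the minimum. A site that respects the minimum leaves out an image that footnote 24 asks for. No text says which rule gives way.

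**Working it through.** **Step 1: the plan's own schedule.** Planned dental gaps for new patients from baseline are 24, 28, 52, 52 and 48 weeks. The limits are 22 to 28 weeks in the first year and 46 to 52 thereafter, so all gaps comply. Bone images are due "at 12 weeks, 24 weeks, 36 weeks, 52 weeks, 76 weeks, 104 weeks, 128 weeks, 156 weeks, and every 24 weeks thereafter", giving gaps of 12, 12, 12, 16, 24, 28, 24, 28 and 24 weeks. The limits are 10 to 16 and then 22 to 28, so these comply too. The problem arises only when an EoT image is added.

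**Step 2: worked example (weeks).**
- Last panoramic x-ray 52, EoT 101: 101 − 52 = 49 > 24, so an EoT x-ray is due.
- Next planned x-ray 104: 104 − 101 = 3 ≤ 4, so the visit is skipped but its imaging is kept.
- Interval between the two x-rays: 3 weeks, against a minimum of 46.

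**Step 3: general condition.** Let L be the last image, E the EoT visit and N the next planned image.
- An EoT image is due when E − L > 24.
- Footnote 24 explicitly keeps the next image when N − E ≤ 4.
- Both hold for a stretch of min(4, (N − L) − 24) weeks before N, and the two images are then at most 4 weeks apart.

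| Dental gap | EoT weeks affected | Interval to next image | Minimum |
|---|---|---|---|
| 24 to 52 (28 wk) | 48.1 to 51.9 | 0.1 to 3.9 | 22 |
| 52 to 104 (52 wk) | 100 to 103.9 | 0.1 to 4 | 46 |
| 104 to 156 (52 wk) | 152 to 155.9 | 0.1 to 4 | 46 |
| any 48-wk gap | last 4 weeks | 0.1 to 4 | 46 |

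**Step 4: size.** Assume stopping times are uniform after year 1 and imaging is planned at a clinic visit. The affected share of stop times is 4/52 = 7.7% on 52-week gaps and 4/48 = 8.3% on 48-week gaps.

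**Step 5: visit windows.** If same-day imaging is not possible, Section 6.2.2 allows EoT imaging in the week before or after the visit. Footnote 23 allows 1 week either side of a planned time point.
- EoT at week 102: windows 101 to 103 and 103 to 105 meet at week 103.
- EoT at week 101: windows 100 to 102 and 103 to 105 do not meet.

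If one image may count for both, only an EoT 2 to 4 weeks before the planned date forces two images: 2/52 = 3.8% to 2/48 = 4.2%.

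**Step 6: bone imaging (minimum 10/22 weeks).** Under footnote 24 the stretch is zero for gaps of 24 weeks or less.
- In the 28-week gaps (76 to 104 and 128 to 156) it is 4 weeks. Over weeks 52 to 156 that is 8/104 = 7.7% of stop times.
- In the 48-week gaps from age 19 it is 4/48 = 8.3%.

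**Step 7: two related mismatches.**
- The counterpart of the planned-imaging sentence in Section 6.2.2 names MRI and dental examinations only. It omits the x-ray and dental imaging that footnote 24 names.
- Table 1.4.2:1 gives the EoT look-back for bone imaging as 12 weeks in the first year and 24 thereafter. Footnote 24 and Section 6.2.2 give 24 throughout. Under the 12-week version, a new patient imaged at week 36 with EoT at weeks 48.1 to 51.9 would have bone images 0.1 to 3.9 weeks apart, against a minimum of 10.

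**The case against.** The best defence is that the minimum was written for regular follow-ups. In footnote 23 it qualifies the window around planned time points, and in Section 5.2.6 it qualifies how follow-ups are planned. EoT has its own look-back, which Table 1.4.2:1 sets beside the minimum. This stands for the EoT image itself. A reader might infer that an EoT x-ray taken 24 to 46 weeks after the last one breaks the minimum on its own. The documents do not support that, because a specific EoT rule stated alongside a general one is not a contradiction. The defence does not cover the second image, which is a regular planned follow-up. Section 5.2.6 and Table 1.4.2:1 count the interval from the previous procedure without excluding an EoT image.

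The clause on individual adaptation is a fair point in part. A change made under it conforms to the protocol, so deviations are not inevitable. But it is discretionary and sets no default for sites.

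The visit windows could absorb about half of the affected stop times, as in Step 5, but only if one image may serve for both, and no text says so.

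Section 6.2.2 omits dental imaging from its version of the sentence, so the panoramic x-ray conflict rests on the wording of footnote 24. That limits the support for the point, but it is also a mismatch to resolve.

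For bone imaging the radiation argument is weak. MRI is the primary method (Section 5.2.5), and x-ray is used only where MRI cannot be done. The dental clinical examination has no minimum interval and is not affected.

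**Conclusion.** The conflict is in the text and is narrow. It concerns patients who stop treatment early, remain in follow-up, have a last panoramic x-ray more than 24 weeks old, and have EoT in the 4 weeks before a visit with a planned x-ray. For them footnote 24 gives two x-rays at most 4 weeks apart, against 46 weeks (22 in the first year). The size is up to about 8% of stop times after year 1, or about 4% if one image can count for both. These are shares of assumed uniform stopping times, not of patients; the documents give no distribution of stopping times.

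Two larger readings should not be drawn:
- A reader might infer that about half of stop times are affected, since (52 − 24)/52 = 54% and (48 − 24)/48 = 50% of them call for an EoT x-ray. Footnote 24 explicitly keeps the next image on its date only within the 4-week window. Outside it, the text asks for one more regular image without fixing its date relative to the EoT image.
- A reader might infer that the safety results would be distorted. In the visible SAP (Section 7.8.1.4), imaging findings enter only as adverse events in the standard tables and listings, so no such effect is shown.

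Sample size and error rates are not involved; the trial is descriptive.

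**What to change.** Reconcile footnote 24 and Section 6.2.2 with footnotes 21 and 23, Sections 5.2.5 and 5.2.6 and the radiation row of Table 1.4.2:1. In the same words in each place, state:
- whether the minimum interval applies between an EoT image and the next planned image;
- whether one image taken within the allowed windows can serve as both;
- which procedures the planned-imaging sentence covers, so that footnote 24 and Section 6.2.2 agree;
- one EoT look-back for bone imaging, so that Table 1.4.2:1, footnote 24 and Section 6.2.2 agree.

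The sponsor decides which rule governs; no imaging interval is proposed here. The cost is amendment wording in these places, with no added procedure.

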β-HCG	Beta- Human Chorionic Gonadotropin
BI	Boehringer Ingelheim
CA	Competent Authority
chILD	Childhood Interstitial Lung Disease
cHP	Chronic Hypersensitivity Pneumonitis
CNS	Central Nervous System
COHb	Carboxyhaemoglobin
COVID-19	Coronavirus Disease 2019
CRA	Clinical Research Associate
CRF	Case Report Form, paper or electronic (sometimes referred to as “eCRF”)
CRO	Contract Research Organisation
CSF1R	Colony-Stimulating Factor 1 Receptor
CT	Computed Tomography
CTCAE	Common Terminology Criteria for Adverse Events
CT Leader	Clinical Trial Leader
CT Manager	Clinical Trial Manager

CTP	Clinical Trial Protocol
CYP3A4	Cytochrome P450 3A4
Δ	Delta, i.e. difference
d	Day(s)
DBL	Database Lock
DILI	Drug Induced Liver Injury
D _{LCO}	Diffusing Capacity of the Lung for Carbon Monoxide
DM	Dermatomyositis
DMC	Data Monitoring Committee
EC	Ethics Committee
ECG	Electrocardiogram
eCRF	Electronic Case Report Form
eDC	Electronic Data Capture
EDTA	Ethylenediamine-Tetraacetic Acid
EOs	End of Study (corresponds with End of Trial)
EOt	End of Treatment
EudraCT	European Union Drug Regulating Authorities Clinical Trials Database
FGFR	Fibroblast Growth Factor Receptor
FUP	Follow-up
FVC	Forced Vital Capacity
GCP	Good Clinical Practice
GFR	Glomerular Filtration Rate
GGT	Gamma-Glutamyl Transferase
GI	Gastro-Intestinal
GLI	Global Lung Initiative
GMP	Good Manufacturing Practice
HA	Health Authority
Hb	Haemoglobin
HP	Hypersensitivity Pneumonitis
HRCT	High-Resolution Computed Tomography
HSCT	Haematopoietic Stem Cell Transplant

i.v	Intravenous
IB	Investigator's Brochure
ICH	International Council on Harmonisation
IEC	Independent Ethics Committee
ILD	Interstitial Lung Disease
IMP	Investigational Medicinal Product
INR	International Normalized Ratio
IPD	Important Protocol Deviation
IPF	Idiopathic Pulmonary Fibrosis
IRB	Institutional Review Board
IRT	Interactive Response Technology
ISF	Investigator Site File
IUD	Intrauterine Device
IUS	Intrauterine Hormone-Releasing System
Lck	Lymphocyte-specific Tyrosine-protein Kinase
LFT	Liver Function Test
LPLT	Last patient last treatment
Lyn	Tyrosine-protein Kinase Lyn
MACE	Major Adverse Cardiovascular Events
MCTD	Mixed Connective Tissue Disease
MCV	Mean Corpuscular Volume
MedDRA	Medical Dictionary for Drug Regulatory Activities
MRI	Magnetic Resonance Imaging
n.a.	Not Applicable
NSIP	Non-Specific Interstitial Pneumonia
OPU	Operative Unit
PIP	Pediatric Investigational Plan
PAH	Pulmonary Arterial Hypertension
PBMC	Peripheral Blood Monocytic Cells
PDGFR	Platelet-Derived Growth Factor Receptor
PF-ILD	Progressive Fibrosing Interstitial Lung Disease

P-gp	Permeability Glycoprotein
PM	Polymyositis
PT	Prothrombin Time
PTM	Planned Time
Q	Quaque i.e. every
q.d.	quaque die (once a day)
RA	Regulatory Authority
RA-ILD	Rheumatoid Arthritis associated ILD
RBC	Red Blood Count
REP	Residual effect period
SAE	Serious Adverse Event
SARS-CoV2	Severe Acute Respiratory Syndrome Coronavirus 2
SFTPC	Surfactant Protein Deficiency
SI	International System of units
SMC	Safety Monitoring Committee
SMQ	Standard MedDRA Query
SOP	Standard Operating Procedure
Src	Proto-oncogene Tyrosine-protein Kinase
SSc-ILD	Systemic Sclerosis associated ILD
SUSAR	Suspected Unexpected Serious Adverse Reactions
TKI	Tyrosine Kinase Inhibitor
TMF	Trial Master File
TS	Treated Set
TSAP	Trial Statistical Analysis Plan
ULN	Upper limit of normal
US	United States
VEGFR	Vascular Endothelial Growth Factor receptor

WOCBP

Woman of childbearing potential

1. INTRODUCTION

1.1 MEDICAL BACKGROUND

Childhood interstitial lung disease ‘chILD’ syndrome’ is a term used to describe diffuse lung disease in children with non-specific respiratory symptoms. It consists of a heterogeneous group of rare respiratory diseases associated with varying morbidity and mortality [[R09-5337](#)]. Although many of the ILDs present in children can also be found in adults, some chILDs are specific to paediatric populations and involve different pathophysiology.

While the pathophysiology underlying most of the pediatric ILD have not been fully characterized, according to the expert opinion, the following diagnoses were considered to be most likely associated with chronic fibrosis and as such potentially amenable to anti-fibrotic treatments:

surfactant protein deficiency (SFTPC and ABCA3 mutations [i.e. recessive disorder, suspected pathogenic variants or deletion/disruption]);

chronic hypersensitivity pneumonitis (cHP);

toxic/radiation and drug induced pneumonitis;

post haematopoietic stem cell transplant (HSCT) fibrosis;

connective tissue disease related disorders (e.g. juvenile rheumatoid arthritis [RA]/ juvenile idiopathic arthritis, SSc, dermatomyositis/polymyositis [DM/PM]; mixed connective tissue disease [MCTD]), sarcoidosis.

There are no currently approved therapies for the treatment of ILD in children. Clinical management is focused on supportive care (e.g. oxygen therapy, ventilator support).

Therapeutic treatment is primarily based on anecdotal evidence, such as case series and clinical observation. Based on the mode of action of nintedanib and its demonstrated effects in adult IPF and other chronic fibrosing ILDs with progressive phenotype, the use of nintedanib in fibrotic ILDs in children was considered to be of potential benefit.

As the underlying diseases associated with the clinically significant fibrosing Interstitial Lung Disease may be multiple, different regimes of immunosuppressives/ supportive symptomatic therapy are considered as standard of care for the treatment of ILD in children.

In the Phase III trial, InPedILD[®] (BI trial 1199-0337; EudraCT no. 2018-004530-14), the parent trial to this open label study, the dose-exposure relationship and safety of nintedanib in children and adolescents with fibrosing ILD was investigated and information on the efficacy was collected as well. In the parent trial, following completion of the 24-week blinded, placebo-controlled treatment period (Part A) patients entered a variable, open label treatment period (Part B). Once 30 patients (including at least 20 patients of age 12-17 years) completed PK at week 26, or prematurely discontinued, the first database lock was announced (DBL1).

As, the benefit/risk assessment based on the data of the InPedILD[®] trial justified further exposure to nintedanib, all patients still on treatment were offered to participate in this open label trial InPedILD[®]-ON (BI trial 1199-0378). Rollover of eligible patients from InPedILD[®]

study to the current trial was planned to occur without treatment interruption, whenever possible [[c26450188](#)].

